8.1.2 Control Intervention (stan dard/routine/comparator treatment / medical device)

The Reference Medical Device (RMD) is the standard hearing aid fitting software used by an HCP. Normally, after they have completed a manual hearing test the HCP enters the results into the fitting software to perform the fitting. The intended purpose is the same; however, the IMD is automated and the RMD is manual. For the purposes of this trial the fitting process is the focus and not the hearing aid output. The standard audiogram results will only be used for inclusion/exclusion criteria and as a control. The fittings with both the IMD and the RMD will use the hearing screening results from the IMD to calculate the fitting targets. The resulting amplification will be the same from both devices. The hearing aids will be programmed only with the IMD screening results in order to reduce variability in the analysis.

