	
 
If the hearing loss is conductive or mixed it must first be approved for amplification by a physician
 

	All shapes of hearing loss (flat, sloping, reverse slope, notch)
	

Severity ranging from mild to severe

First time hearing aid users (never worn hearing aids before)

	German speaking
	Both genders
	
 
Ages 18 and older
 
Ability and willingness to sign the consent form
 

	Exclusion Criteria:
	Current hearing aids users
	
 
Contraindications for amplification
 
Active ear disease
 

	
 
Inability to follow the procedures of the study due to language problems, psychological disorders, dementia, or other cognitive
 

	
 
problems of the participant
 
A reduced mobility unable to attend weekly study appointments
 
A reduced ability to describe auditory impressions and the usage of the hearing aids
 

	
 
Uncooperative so that it is not possible to record a valid pure tone audiogram
 

	

A strongly reduced dexterity

With psychological problems

	
 
With psychological problems
 
Central hearing disorders
 

	

Bernafon employees

Family members of Bernafon employees

Measurements and procedures:	A hearing test will be made using standard audiometry performed by the investigator and a hearing screening using the new self-directed software which includes an automated screening. Amplification is fitted either using the first fit procedure with the standard Oasis software (RMD) or with the new self-directed software (IMD) that uses a simplified version of the existing Oasis software. First fit in the context of this trial will mean without any additional fine tuning. During a normal first fit it is possible to make changes based on subject comments. However, to maintain that the acoustic fitting of the two sets of hearing aids is the same there will be no fine tuning performed.

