# 6. STUDY DESIGN

### 6.1 General study design and justification of design

This is a controlled, randomized, open label, cross-over, comparative clinical investigation conducted at two sites within Canton Bern, Switzerland.

The exploratory study is based on a population of hearing impaired people that have hearing loss appropriate for the hearing aids.

As a control, the RMD will be used to fit the hearing aids as well as the IMD. Additionally, a control situation will be implemented by using an unaided test condition in laboratory speech testing.

There is no placebo or "fake" device that does not provide amplification. A randomized cross-over design will be used with one group using the device programmed with the RMD first and the other using the device programmed with the IMD and then switching. The testing will be unblinded as the subjects can clearly see a difference between fitting methods. Although two hearing tests will be completed (standard audiometry and IMD screening), the hearing aids will be programmed only with the IMD screening results in order to reduce variability in the analysis of the results. Therefore, the hearing aids will be acoustically programmed the same, but this will not be explained to the participants.

The same randomized test order will be used to test in a simulated environment. At the end of the field test period the participants will return to the clinic. They will be given a speech test in the unaided condition and the aided condition with the hearing aids as they have worn them for the previous 10 days. They will then be fit with the other method (whichever they did not have in the first round), and then have speech testing again in the aided and unaided condition at the end of the field test period.

The participants will be expected to participate for approximately 1 month for a combination of field tests and lab tests. For lab tests they will not spend more than 1.5 hours in the clinic for testing. They will be expected to come for 3 visits in total. Field trial periods will not last more than 10 +/-5 days.

The sequence will begin with the screening visit which will also be the first intervention visit if they satisfy the inclusion criteria and if they choose to join the study. The entire test procedure will be explained, and they will be given a Patient Informed consent form to read which will need to be signed, dated, and returned before any trial procedures begin.

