#### 8.1.1 Experimental Intervention (treatment / medical device)

The investigational product (IMD) is a medical device. It is a new self-directed software that combines a hearing screening and the hearing aid fitting into one procedure. The name of the software is HearToo Studio. The hearing aid that the software will program for the trial is already CE marked and sold on the market for 2 years. It still has the same intended use and the basic function of amplifying sound.

The IMD will produce automated tones at a frequency range of 250 Hz to 8000 Hz with an output limit of 80 dB. A standard audiometer has an output of up to 120 dB at certain frequencies. The IMD only has an output of 80 dB to mitigate the risk of a person allowing the system to present too loud of tones by not responding. The user will respond when they hear the tone. The IMD transfers the screening results to a restricted version of Oasis software to implement the results into the hearing aid fitting. Traditionally, these results are input manually by the HCP into the software. The software will use the screening results to quantify the amount of amplification needed in the hearing aid in the same manner that it does in the current Oasis software. Performance is expected to be the same when programmed with the IMD as it is with the RMD because both fitting methods will use the IMD screening results to calculate gain. The hearing aids when programmed with either method will be the same electro-acoustically.

The version of Oasis software is a restricted and simplified version. There will only be 3 styles of hearing aids offered and one type of acoustics. Therefore, decisions that HCPs would normally have to make with the standard software have been removed and are automatically chosen in the software. The HCP cannot fit multiple programs to the hearing aid with the IMD, only one. They also can make simple fine-tuning as seen in the picture below. In the standard version of the software the HCP can adjust specific frequencies and input levels, as well as adjust features.

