### 8.2 Admini stration of experimental and control interventions

#### 8.2.1 Experimental Intervention

At the first visit the participants will complete a hearing test using standard audiometry performed by the clinician and a screening using the IMD. The standard audiometry is used as a base test for the inclusion/exclusion criteria and as a control measure for the screening results of the IMD. The hearing devices will be programmed using both the RMD and the IMD during the course of the trial. The screening results from the IMD will be used for both fittings to ensure that the acoustic output of both methods is the same. The difference in the fitting process of the RMD and the IMD is the focus of the trial and not the actual output of the hearing aid.

The IMD will present tones from 250 Hz to 8000 Hz, and the participants will indicate when they've heard the tone. The tones are directed into the ears of the participants with supra-aural headphones. The test should take no more than 15 minutes. Depending on the randomization assignment, some participants will then start the fitting portion of the IMD. Hearing instruments will be connected using a wireless neck loop that the subjects will wear. Once the fitting has been programmed into the hearing aids the investigator will place the hearing aids in the subject's ears. The fitting process should not take more than 20 minutes. They will wear the programmed devices for approximately 10 hours per day for an overall time of approximately 20 +/-10 days for the trial. There are no surgical techniques used in the application of this device. It is a non-invasive device.

The study procedure will use a cross over design with two groups. One group will wear the hearing aids fitted with the IMD and one will wear the hearing aids fitting with the RMD. After 10 days they will switch to whichever method they did not have previously. As stated, the device is non-invasive and requires no surgical procedure. The device sound port will be inserted into the ear and the body of the device placed behind the ear each morning by the subjects themselves and removed each night by the subjects themselves. There is minimal training needed for a first time user to learn how to insert a hearing device. The subjects will be given an Instructions for Use booklet that explains how to insert the device and provides further instructions concerning cleaning, battery changing, and warnings.

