#### 8.2.2 Control Intervention

The hearing screening results achieved from the IMD will be manually entered into the standard Oasis software for the fitting with the RMD. The hearing aids will be connected to the software using the same wireless neck loop used for the programming with the IMD. The investigator will fit the hearing aids and then place them in the subject's ears.

The subject will then wear the hearing aids for 10 days. The device will be inserted into the ear and placed over the ear each morning by the subjects themselves and removed each night by the subjects themselves. There is minimal training needed for a first time user to learn how to insert a hearing device. The subjects will be given an Instructions for Use booklet that explains how to insert the device and provides further instructions concerning cleaning, battery changing, and warnings.

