### 9.3 Procedures at each visit

#### Visits to Clinic

#### 9.3.1 Screening Visit/First Visit

Screening visit, Day 0: The trial will be explained including how many visits are expected as well as the type of testing that they will complete. They will be given the Patient Information sheet and everything explained to them by the site investigator. Subjects are given time during the appointment to decide, whether or not to participate in the study. If they choose to not take part in the trial they will not sign the consent form and the appointment will finish. They can still follow-up with the clinic for a standard hearing aid purchase if they choose. If they choose to join the trial they will sign and date the Patient Informed consent form. No trial activities will be performed before the Patient Informed consent form is signed and dated by the subject and investigator. Subjects will receive a copy of the signed patient informed consent form and the patient information. A hearing history is then taken and otoscopy is performed. The initial hearing test is performed to determine hearing loss including air and bone audiometry. Inclusion/exclusion criteria will be determined. The subjects will then complete a questionnaire to quantify their perceived hearing loss handicap (Gothenburg). They will complete a hearing screening using the IMD. Based on the randomization plan they will be fitted with hearing aids either with the IMD or the RMD. The investigator will make no fine tuning of the fittings. Gain and features will be set as prescribed by the software. They will receive an Instructions for Use (IFU) for the They will be given a standardized questionnaire (IOI-HA) and a custom product hearing aid. questionnaire to fill out during the first period of the field trial. The HCP will review the questionnaires to ensure that the subjects understand their task. They will be scheduled for the Second Visit. Any AEs will be reported in the CRFs.

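### Both fittings rest on the IMD screening alone, and no protocol step requires acting on a gross disagreement with the standard audiogram before aids are issued (low severity, cheap to fix)

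*Protocol*

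**What the plan says.** **Source of gain.** Protocol 6.1 states that "the hearing aids will be programmed only with the IMD screening results in order to reduce variability in the analysis of the results". Section 8.1.1 repeats that "both fitting methods will use the IMD screening results to calculate gain", and section 8.2.2 describes the control fitting: "The hearing screening results achieved from the IMD will be manually entered into the standard Oasis software for the fitting with the RMD".

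**No later correction.** The synopsis says that "there will be no fine tuning performed", and sections 9.3.1 and 9.3.2 repeat this for Visits 1 and 2. Section 8.1.1 mentions simple fine tuning, but as a capability of the software and not as something the trial allows.

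**Role of the standard audiogram.** Section 9.3.1 places it early in Visit 1: "The initial hearing test is performed to determine hearing loss including air and bone audiometry". Section 8.1.2 then confines it: "The standard audiogram results will only be used for inclusion/exclusion criteria and as a control". Section 8.2.1 describes it "as a control measure for the screening results of the IMD", with no limit and no action attached. The planned comparison of the two sets of thresholds is a secondary analysis (Protocol 11.4.3, SAP 2.2.1), run once all participants have completed (Protocol 11.3).

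**Range of the screening.** Section 8.1.1: "The IMD will produce automated tones at a frequency range of 250 Hz to 8000 Hz with an output limit of 80 dB". Section 7.1 admits losses from mild to severe and does not define severe in dB.

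**The concern.** A grossly wrong screening would go straight into the aids, although the result that would expose it is already on file from the same visit. The error could run in two directions. If a participant fails to respond to audible tones, the recorded threshold is too high and the prescribed gain would tend to be too high. If the true loss exceeds the 80 dB limit, the recorded value may be too low and the gain would tend to be too low. Both statements assume that the software prescribes from the recorded or limiting value. The documents do not say how it handles a non-response at 80 dB.

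Protocol 3.4 names an incorrect screening result caused by background noise as the primary identified risk, and sets it aside because testing is in a clinic. A clinic controls noise. It does not by itself prevent missed responses or remove the 80 dB limit.

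What is at stake is a field period of about 10 days on wrong gain, and a second one if Visit 2 does not pick it up, because the same thresholds are used again. Such a case is also an IMD performance finding, which a pre-release validation (Protocol 4.1, 4.2 and 4.4) should capture when it occurs.

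**Working it through.** **Step 1: order of events at Visit 1 (Protocol 9.3.1).** Standard air and bone audiometry; eligibility; Gothenburg questionnaire; IMD screening; fitting as randomised. No comparison of the two audiograms stands between the last two steps.

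**Step 2: does another provision require it?**

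| Provision | What it does | What it leaves open |
|---|---|---|
| 7.1 exclusions (no valid pure tone audiogram, cognitive problems, strongly reduced dexterity, poor ability to describe auditory impressions) | Removes people likely to give unreliable responses | Says nothing about the IMD result itself |
| 3.4 clinic setting; 3.2 consultant assistance | Reduces noise and user error | No comparison required |
| 9.2.4 reporting of uncomfortable sounds during screening and fitting | Can act before the participant leaves | Depends on the participant; less likely to reveal too little gain |
| 7.4 withdrawal for unreliable responses | Allows the investigator to stop | Discretionary; not tied to the audiogram |
| Synopsis, electro-acoustical control | Concerns equal gain from the two methods | Two equally wrong fittings would agree |
| 8.2.2 manual entry | Staff see the screening values | RMD fitting only; no check stated |
| 11.5 removal of doubtful data | Acts on data | Does not act on the aids |
| 8.3 removing the aids; 9.3.2 speech test at Visit 2 | May limit or reveal a problem | Both come after issue |

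None of these makes a disagreement with the standard audiogram a reason to act before issue.

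**Step 3: can the rate be computed?** No. The documents give no rate of gross screening error, no dB definition of severe and no rule for a non-response at 80 dB. They state no figure on this point to reproduce.

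**Step 4: what would a trigger cost under ordinary disagreement?** This measures the workload of the remedy, not the size of the problem.

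Inputs: between-method SD 6.4 dB (Protocol 3.4); mean differences of -3 dB at 250 Hz, 3.6 dB at 8000 Hz and about 0.1 dB overall (SAP 2.2.1); minimum 24 and maximum 40 participants. Assumptions: the SD applies to single thresholds, differences are normal, and each person has k = 12 to 16 thresholds over two ears.

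- Per threshold, 20 dB limit, zero mean: p = 2 × (1 − Φ(20/6.4)) = 2 × (1 − Φ(3.125)) = 0.00178.
- Per person, independent errors: 1 − (1 − p)^k = 0.0211 (k = 12) to 0.0281 (k = 16). Times 24 = 0.51 to 0.67; times 40 = 0.85 to 1.12.
- Within-person correlation 0.5 (equicorrelated normal errors, numerical integration): 0.0173 to 0.0219. Times 24 = 0.42 to 0.53.
- Perfect correlation: 0.00178. Times 24 = 0.04.
- Mean shifts only where reported, and 0.1 dB elsewhere, independent errors: p = 0.00531 at 8000 Hz, 0.00411 at 250 Hz and 0.00178 elsewhere. Then 1 − (1 − 0.00531)² × (1 − 0.00411)² × (1 − 0.00178)^(k−4) = 0.0326 to 0.0395. Times 24 = 0.78 to 0.95; times 40 = 1.30 to 1.58.
- 15 dB limit, zero mean, independent errors: p = 0.0191; per person 0.207 to 0.265. Times 24 = 4.96 to 6.37.

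A 20 dB limit therefore refers about one or fewer of 24 participants on ordinary disagreement. A 15 dB limit refers about five or six.

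**The case against.** Using one set of thresholds for both fittings, without fine tuning, is deliberate and sound. It holds gain constant so that a difference in ratings can be attributed to the fitting process. That stands, and the point does not dispute it.

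The stronger objections concern evidence. No harm is quantified, and every number above describes the proposed trigger. If thresholds are recorded in 5 dB steps (an assumption; no step size is given), more than 20 dB means at least 25 dB. Taking 22.5 dB as the rounding boundary, the zero-mean independent workload falls to about 0.13 to 0.17 of 24. The direction of the gain error depends on undocumented software behaviour. The exclusions in Protocol 7.1 and the in-visit reporting in 9.2.4 address likely causes of gross error. All of this stands and keeps the severity low. It does not supply the missing step.

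A reader might infer from Protocol 3.4, where 55% completed a similar self-directed process without errors, that the remaining 45% had wrong thresholds. The text does not support that. It does not say how many errors changed a threshold, and a consultant assists here. The figure shows only that user error is foreseeable.

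The Investigator's Brochure and the Risk Assessment were not available, so a rule held there cannot be excluded.

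**Conclusion.** The point holds as a low-severity, inexpensive safety improvement. In the supplied protocol both fittings depend on the IMD screening alone, the standard audiogram is confined to eligibility and control, and nothing requires action on a gross disagreement before aids are issued. The frequency and the harm of such cases cannot be computed from the documents.

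Two stronger conclusions are not supported. One is that the IMD-RMD comparison is biased: a screening error enters both periods equally, so it does not favour either method. The other is that participants are likely to be harmed: existing safeguards lower the risk, and no rate is available.

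The workload estimate of about one or fewer of 24 at a 20 dB limit rests on the 6.4 dB SD applying to single thresholds, normal errors and 12 to 16 thresholds per person. User error and losses above 80 dB would add an unknown number.

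**What to change.** In Protocol 8.1.2 and 9.3.1, add that before aids are issued the fitting investigator compares the two Visit 1 audiograms. If any threshold differs by more than a prespecified limit (for example 20 dB, for the sponsor to confirm), aids are by default not issued on that screening unless the investigator documents why fitting is acceptable. Placing the decision with the fitting investigator, with a stated default, suits four investigators at two sites.

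Record a non-response at 80 dB and judge it against the standard audiogram under the same limit; do not refer it automatically. Keep the first IMD screening in the audiometry analysis, and report every triggered case and its outcome as an IMD performance or safety finding. The CRF list in section 12.1.1 names neither audiogram, so adding both, with the decision, would help. If the Investigator's Brochure or Risk Assessment already contains such a rule, cite it in the protocol instead.

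**Cost.** A couple of protocol sentences and a short comparison at Visit 1, with no new test. Aids that are issued still use IMD thresholds in both periods, so the equal-gain design is kept. The downside is that a few fittings may be delayed or not made. That slightly selects the complete-case set (section 11.5) and keeps some IMD failures out of field use. Reporting every triggered case keeps this visible.

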Number of Participants with Rationale:	There will be an exploratory analysis of data only. The total number of participants will be a minimum of 24 (no more than 40), and the explanation for this sample size is as follows:
	A literature search about this tested topic does not provide enough strong references to build a confirmatory analysis. It seems that results might be strongly influenced by the inclusion criteria (first time vs experienced hearing aid users) or test design (cross-over, multi-investigator, or between group designs). There is no article to our knowledge that includes a multi-investigator effect in the test design when looking at the effect of different fitting procedures. Adding a treatment interaction term seems to be mandatory if this trial wants to determine the effect that different investigators may have. Each investigator shall treat the same amount of subjects.
	The 24-40 subjects will participate in 2 field studies, but randomized into different fitting/intervention groups with half the number of subjects in each group.
Study Duration:	Approximately 3 months
	The screening of the participants will begin in February of 2018 and the final data collection appointments will occur in April 2018.
Study Sched ule:	The first participant is expected to begin in February 2018.
	The last participant is expected to finish the testing in April 2018.
Investigator(s):	[name], Research Audiologist, Doctor of Audiology
	[name]
	[contact] [contact]
Study Centre(s):	The testing will be performed at two clinical sites in canton Bern, Switzerland.
Statist ical Consider ations:	The analysis and documentation will be performed by the statistician using the latest validated R version with R Studio as IDE. Appropriate data analysis will be performed with parametric and non-parametric tests on questionnaire outcomes, hearing threshold measures, and speech test scores.

GCP Statement:	This study will be conducted in compliance with the protocol, the current version of the Declaration of Helsinki, the ICH-GCP or ISO EN 14155 (as far as applicable) as well as all national legal and regulatory requirements.
	Tal as applicable) as well as all flational legal and regulatory requirements.

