### 3.4 Clini cal Evidence to Date

A clinical literature evaluation is maintained and has been updated in 2016 for the hearing aids. They are designed to amplify sound. The benefit of hearing aids has been shown in various studies (Kochkin, 2011). The evaluation includes an analysis of adverse events for Bernafon products as well as competitor devices. The basic benefit of hearing aids does not change with newly released devices.

A new literature search was completed in June of 2017 specifically for self-directed hearing test and fitting devices. In 2013 a study was completed by Eikelboom et al. to compare the results of standard audiometry to an Automated Method for Testing Auditory Sensitivity (AMTAS) system. The standard deviation between methods across frequencies was 6.4 dB. Using standard audiometry a 5 dB test retest difference is acceptable. The 6.4 dB difference using an AMTAS system is slightly higher than the expected but not significant. According to a study by Convery et al. (2015), self-directed hearing tests show good test-retest reliability. Also, a study was completed by Convery et al. (2017) with a combination system similar to the IMD in which subjects completed a self-directed hearing test and fitting. Fifty-five percent were able to complete the process with no errors at all. The results show the importance of good training material.

A risk assessment is performed for all new devices. The primary risk identified is the possibility of achieving incorrect screening results if there is too much background noise. For the study purposes the test will be completed in a clinic; therefore, this risk is not applicable. However, in everyday use the environment in which the system is used cannot be controlled. The risk is mitigated by providing training material for the consultant that describes the type of environment needed to run the hearing screening. Additionally, no adverse events for any currently marketed self-fit hearing instrument systems have been reported.

The current study will provide further data for self-directed hearing tests and fitting systems.

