# 4. STUDY OBJECTIVES

### 4.1 Overall Objective

The purpose of this study is to compare the performance of the IMD to the RMD. The study aims to provide a final validation and quality control of the IMD before it is released for sales.

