#### 4.2 Primary Objective

The study seeks primarily to determine if the subjective benefit of the hearing aids fitted with the IMD is as good as the RMD. Does one fitting method provide a psychological effect that influences the participants? As a second primary objective the study seeks to proactively determine if there is any unknown and/or unwanted behavior from the IMD. The study seeks to validate that the performance of the IMD is not inferior to the RMD.

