### 9.1 Study flow chart(s) / table of study procedures and assessments

\*Depending on randomization subjects will be fit with IMD at the first or second visit. Everyone will use the IMD at the first visit to perform audiometry.

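### The IMD–RMD comparison cannot show that IMD performance is not inferior: both fittings use the IMD's screening thresholds, and no margin is set

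*Protocol*

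**What the plan says.** **What the device is.** Protocol 8.1.1 on the IMD: "It is a new self-directed software that combines a hearing screening and the hearing aid fitting into one procedure". Protocol 8.1.2 on the standard method: "Normally, after they have completed a manual hearing test the HCP enters the results into the fitting software to perform the fitting".

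**What the trial does.** Protocol 8.1.2: "The fittings with both the IMD and the RMD will use the hearing screening results from the IMD to calculate the fitting targets". Sections 6.1, 8.1.1, 8.2.1 and 8.2.2 say the same. The investigator's audiogram serves eligibility and control only, so no aid is ever programmed from it. Section 8.1.1 gives the shared thresholds as the reason for expecting equal performance.

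**What is to be concluded.** Protocol 4.1: "The study aims to provide a final validation and quality control of the IMD before it is released for sales"; the opening of section 11 repeats this. Protocol 4.2: "The study seeks to validate that the performance of the IMD is not inferior to the RMD".

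**Status of the analysis.** Synopsis, number of participants: "There will be an exploratory analysis of data only". Protocol 11.2 and SAP 3 add that the literature is too weak for a confirmatory analysis.

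**The separate check of the screening.** IMD thresholds are compared with standard audiometry as a secondary outcome (Protocol 5.2, 9.2.2, 11.4.3; SAP 2.2.1). Equivalence of the two is the second of two research questions (Protocol 11.1; SAP 1.1). The named methods are a nested model of threshold differences and a paired t-test (Protocol 11.4; SAP 4.1). No acceptance limit is given.

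**The concern.** The stated conclusion is wider than the comparison behind it. Of the IMD's two parts, only the fitting step differs between conditions; the screening is common to both. Similar IOI-HA, speech or preference results are therefore to be expected however good or bad the screening is.

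Protocol 3.4 names incorrect screening results as the primary risk in the device's risk assessment, through background noise in everyday use. If a null IMD–RMD result were reported under 4.2 as non-inferior performance, it would be read before release as covering the whole device. It would carry no information on what a wrong threshold does to the user's outcome.

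The one analysis that does address the screening is set up as a test of difference. A non-significant result there could also be taken for equivalence, which it would not be.

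**Working it through.** **1. What the IMD–RMD contrast contains.** For one participant let T be the investigator's threshold, e the IMD screening's departure from it, g the prescription rule (the same in both methods, Protocol 3.1), f the effect of gain on the outcome, and a the effect of the fitting process. Audiometry is scheduled only at Visit 1, so one screening result serves both periods.

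- IMD: Y = f(g(T + e)) + a(IMD)
- RMD as run in the trial: Y = f(g(T + e)) + a(RMD)
- Difference: a(IMD) − a(RMD); the terms in e cancel for any e
- RMD as normally practised: Y = f(g(T)) + a(RMD); the difference would then also contain f(g(T + e)) − f(g(T))

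The additive form is for clarity. If gain and process interact, the contrast is still a process effect at one common gain, and still not a comparison of two gains.

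**2. The plan's power figure.** Inputs (Protocol 11.2, SAP 3.2): w = 0.65, df = 2, n = 24, alpha = 0.05.

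- Noncentrality = n × w² = 24 × 0.4225 = 10.14; noncentral chi-square power = 0.821 (stated 0.82).
- SAP two-category variant: 24 × 0.6² = 8.64, df = 1; power = 0.836 (stated 0.84).

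Both reproduce. They give the power to detect a departure from chance in the preference counts, and say nothing about excluding an inferiority of a given size.

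**3. The missing margin.** Neither document states one for any outcome. For scale only, suppose the SAP's reference result (3.2 IOI-HA points, effect size 0.68) is a paired standardised difference, which is an assumption. Then SD = 3.2 / 0.68 = 4.7. With a true difference of zero, one-sided alpha 0.025 and 80% power (t-based), the smallest margin the trial could support is:

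| SD of paired difference | n = 24 | n = 40 |
|---|---|---|
| 3 | 1.8 | 1.4 |
| 4.7 | 2.8 | 2.1 |
| 6 | 3.6 | 2.7 |

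Even with such a margin, step 1 would confine the conclusion to the fitting process.

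**4. What the paired t-test on thresholds can show.** Protocol 3.4, from a cited study of an automated system: "The standard deviation between methods across frequencies was 6.4 dB". Borrow that SD for one frequency and one ear per participant (an assumption).

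- n = 24: standard error = 6.4 / √24 = 1.31 dB; offsets up to 2.069 × 1.31 = 2.7 dB are non-significant.
- n = 40: standard error = 6.4 / √40 = 1.01 dB; offsets up to 2.023 × 1.01 = 2.0 dB are non-significant.

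The same observed offset of 2.5 dB would thus pass with 24 participants and fail with 40; sample size decides, not a limit of acceptability.

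A mean difference also hides spread. At mean zero, the 95% range of individual differences is ±1.96 × 6.4 = ±12.5 dB. Opposite offsets can cancel too: SAP 2.2.1 reports a mean of about 0.1 dB across frequencies, with −3 dB at 250 Hz and +3.6 dB at 8000 Hz.

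**5. Illustration of between-method disagreement.** With mean 0, SD 6.4 and normality assumed, P(|d| > 5) = 0.435 and P(|d| > 10) = 0.118. About 43% of threshold pairs differ by more than 5 dB and 12% by more than 10 dB.

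**The case against.** **The design is deliberate.** Fixing the gain isolates a narrative effect, and 8.1.2 and 8.2.1 say openly that the process, not the output, is the focus. The first research question is already worded for identical electro-acoustics. This stands. A reader might infer that the RMD should have been fitted from the clinician's audiogram; for the narrative question the documents do not support that.

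**The screening is tested.** A reader might infer that the trial leaves the IMD's main technical risk unexamined. It does not: IMD thresholds are compared with the investigator's audiometry, by plan in every participant, and Protocol 3.1 gives that as the purpose. The final validation in 4.1 could therefore rest partly on that comparison and on safety. This stands, and it narrows the point to which conclusion rests on which evidence. It does not rescue a test without an acceptance limit.

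**Universal screening at Visit 1.** Section 9.1 says: "Everyone will use the IMD at the first visit to perform audiometry". A reader might take this as a further reason why non-inferiority fails. It is not: it may dilute the narrative contrast, because RMD-first participants have already used part of the IMD, but it has no bearing on non-inferiority.

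**The 6.4 dB percentages.** A reader might take 43% and 12% as rates of wrong IMD thresholds. They come from a cited study, not from this software, and they include the retest variation of manual audiometry, for which Protocol 3.4 itself accepts 5 dB. They are illustrative only.

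**It is only exploratory.** The synopsis and 11.2 say so, but 4.1 and 4.2 are not worded that way. This is the inconsistency to resolve.

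**Conclusion.** The point holds as a mismatch between the claim and the evidence, not as a fault in the design. The contribution of screening error to the IMD–RMD contrasts is zero by construction; this needs only that both fittings use the same IMD thresholds and the same prescription rule, and both are stated. Independently, no margin exists and the stated power is for another test. A null result on IOI-HA, speech or preference therefore cannot support the sentence in 4.2.

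The comparison can still answer whether the fitting process changes perceived benefit at identical gain. Evidence on screening accuracy comes only from the threshold comparison, which as planned can detect a mean difference but cannot establish equivalence. The size of any actual IMD threshold error is unknown from the documents, and nothing here shows that it is large.

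**What to change.** Keep the design, visits and fittings as they are.

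1. **Protocol 4.1, 4.2 and the opening of 11.** Limit the IMD–RMD conclusion to the effect of the fitting process on perceived benefit at identical gain. Remove non-inferior performance as a conclusion from IOI-HA, speech or preference. Say which part of the validation rests on the threshold comparison and which on safety.
2. **Protocol 11.4 and 11.4.3, SAP 2.2.1 and 4.1.** Base any statement about the validity of the screening only on the threshold comparison. Report paired differences by ear and frequency, with confidence intervals and limits of agreement, against an equivalence limit that the sponsor fixes and justifies beforehand. The nested model already foreseen can allow for two ears per participant. State how ears with no response at the IMD's 80 dB output limit are handled. A non-significant t-test should not be the criterion.
3. **Data capture.** The CRF list in 12.1.1 names neither set of thresholds; add both.
4. **Optional.** Report, descriptively and without fitting anyone, the difference between the gain Oasis prescribes from the standard audiogram and from the IMD thresholds. State which thresholds are entered: standard audiometry includes bone conduction, the IMD is described only with headphone tones, and conductive and mixed losses are eligible.

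The cost is wording, one justified limit, and a narrower headline claim. The threshold measurements are already scheduled at Visit 1.
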